Laxatives are the main line of maintenance therapy of overflow retentive stool incontinence (ORSI) with satisfying results (**Yik 2012**) stimulant laxatives like senna based laxatives (SBL) are our standard choice in Egypt due to its availability (**Bassiuony 2015**).

Massage is the manipulation of muscles and connective tissues (CT) (superficial and deeper layers) by using different techniques. It has been practiced in many ancient civilizations for thousands of years. (**Weerapong 2005**)

Abdominal massage is a noninvasive, effective, and safe form of constipation management in the general population. (**Lamas et al. 2009, Lamas et al., 2012 and Turan&Asti 2016**) .It provides a low burden of risk, reduces symptoms of chronic constipation, improves the quality of life, decreases the use of laxatives and increases the frequency and consistency of bowel movements (**Smith and Moss, 2008; Moss et al., 2007; Richards 1998; Lamas et al., 2010**).

Subjects and methods:

This randomized controlled study was conducted in the out-patient clinic in the Faculty of Medicine, South Valley University from March 2016 to March 2019. The parents of each child submitted Informed consent. The procedures that followed had No: P.T. REC/012/002277 that approved by the Institutional Ethical Committee Clearance of the Faculty of Physical Therapy at Cairo University. The study had registration number NCT registered on Clinicaltrial.gov.

A total of one hundred and seventy children with overflow retentive stool incontinence were evaluated for eligibility. Twenty-seven children did not complete the treatment course, fifty-eight child excluded due to unresponsiveness or non-compliance to our protocol, and eighty-six child was divided randomly into two groups.

The children were selected according to these criteria: (i) Children's aged ranged from four to fourteen years, (ii) children were from both sexes, (iii) children had a history of overflow retentive stool incontinence. Other children were excluded from our study as they met one of the following criteria: (i) children had suspicion of Hirschsprung's disease, (ii) children had anorectal malformation, (iii) children had organic obstruction, (iv) children failed to complete treatment (if cramping abdominal pain or vomiting occurred), (v) children required bowel surgery.

Group A: Senna based laxative

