Initial cleanout protocol for dis-impaction of the colon with the administration of one or two enemas per day with 20 ccs/Kg warm tap water with a salt enema (0.9 % saline can be made by adding 1.5 teaspoons of salt to 960 ml of water) (**Levitt 2010**) till been clean by radiologically. If initial dis-impaction was failed or not tolerated, shift to dis-impaction under general anesthesia.

Single 10 mg dose senna was given with the start of impaction. After dis-impaction; senna dose was increased if needed by 10 mg/clinic visit/week till achieving no soiling; Documentation of both initial effective starting dose and the time slipped till no soiling. Follow-up visits every month unless soiling recurs if soiling happens; additional dose (by 10 mg) was done. Treatment was continued for 6 months.

At the end of 6 months, the effective ending dose (maintenance dose) was documented.

Group B: Senna based laxative with massage

Laxative treatment as group A in addition to massage technique.

The massage technique was based upon the Tactile Stimulation Method of Birkestad that primarily consists of palm-to-skin stroking, gentle pressure and static touch (**Birkestad 1999**).

The patients lying in a comfortable relaxed supine position and physiotherapist performed slow circular clockwise movements on the abdomen, throw tangential pushing, with digital pulp, slow and gradual pressure, with fingers inclination 45

degrees (**Harrington & Haskvitz 2006**). The pressure applied to the abdomen on each point for 1 min, beginning with the ascending colon, transverse colon, descending colon and sigmoid; this sequence was repeated approximately 15 min. The therapist teaches the parents this technique and asked them to apply at home 3 times/day for 15 min.

Statistical analysis

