The statistical analysis was conducted by using statistical SPSS Package program version 25 for Windows (SPSS, Inc., Chicago, IL). Data were normally distributed by using the Shapiro-Wilk test (parametric data). Additionally, testing for the homogeneity of variance revealed that there was no significant difference ($P>0.05$). Quantitative descriptive statistics included the mean and standard deviation for demographic data (age, weight, height, and BMI), constipation starting dose, constipation end dose, and time till not soiling variables. Qualitative descriptive statistics included number (percentage) for gender, area, breastfeeding, previous incomplete therapy for constipation, full urinary continence, fissure, psychosocial problems, developmental delay, and history of delayed passage of meconium variables. Using paired t-test to compare between rural area and the urban area within massage group and without massage group for constipation starting dose, constipation end dose, and time till not soiling variables. Using independent t-test to compare between massage group and without massage group for demographic data (age, weight, height, and BMI), constipation starting dose, constipation end dose, and time till not soiling variables. Also, to compare between two groups (massage group and without massage group) within the rural area and urban area for constipation starting dose, constipation end dose, and time till not soiling variables. Chi-square test used to compare between massage group and without the massage group for qualitative variables. All statistical analyses were significant at the level of probability ($P \leq 0.05$).

References:

Rasquin A1, Di Lorenzo C, Forbes D, Guiraldes E, Hyams JS, Staiano A, Walker LS. Gastroenterology. 2006 Apr;130(5):1527-37.

Mugie, S. M., Benninga, M. A., & Di Lorenzo, C. (2011). Epidemiology of constipation in children and adults: A systematic review. Best Practice & Research. Clinical Gastroenterology, 25, 3-18.

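### Time till no soiling is compared by t-test with no rule for children who never stop soiling, so the comparison is of speed among successes only and can miss a benefit of massage or be biased in either direction

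*Combined protocol and SAP*

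**What the plan says.** The section on Group A calls for "Documentation of both initial effective starting dose and the time slipped till no soiling". Visits are weekly during titration. Once soiling stops the schedule becomes "Follow-up visits every month unless soiling recurs", and no rule says how a recurrence changes the recorded time. On duration: "Treatment was continued for 6 months". Group B has the same laxative course plus massage.

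The Statistical analysis section summarises "constipation starting dose, constipation end dose, and time till not soiling variables" by mean and standard deviation. The between-arm comparison of these variables is given as "Using independent t-test to compare between massage group and without massage group", and it is repeated within rural and urban areas. The chi-square test covers the qualitative variables, a list that opens "Qualitative descriptive statistics included number (percentage) for gender, area, breastfeeding" and continues with history and comorbidity items. Soiling-free status is not on it.

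Unresponsive children appear only in Subjects and methods, where 58 were "excluded due to unresponsiveness or non-compliance to our protocol". The same paragraph says: "Twenty-seven children did not complete the treatment course". Neither count is split by arm. Eighty-six children are said to have been randomised.

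**The concern.** Time to the first soiling-free visit is a time-to-event outcome with a natural limit at 6 months. A child still soiling then has no time to enter in a t-test and drops out of the comparison, although that child is the treatment failure. Three things follow.

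- A benefit that consists of more children becoming soiling-free cannot be seen in a mean among responders, and no other planned analysis would show it.
- If massage rescues children who respond late, they lengthen the massage-arm mean and the test can turn against massage.
- If slow or non-compliant children are removed more often from the massage arm, massage is flattered. This matters because the Abstract reports a significant result in favour of massage, without naming the outcome.

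**Working it through.** The documents give no sample-size calculation, standard deviation or response rate, so there is no stated figure to reproduce. The check is a simulation under declared assumptions.

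**From the documents:** 86 randomised, significance level 0.05, weekly visits until success, 6 months of treatment.

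**Assumed:** 43 per arm (arm sizes are not given), 26 weekly visits, two-sided testing, and all response rates. Each scenario has 10,000 simulated trials. A t-test among children with a time is compared with a log-rank test on all randomised children, censored at week 26.

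**Calibration.** With no effect and no removal, the type I error is 5.0% (t-test) and 4.8% (log-rank).

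**(a) More successes, equal speed.** Success is 41% versus 60%, and responders succeed with probability 0.25 per week in both arms. Times among responders have the same distribution in both arms, so the t-test can reject only at its 5% error rate. Log-rank power is 41%. Hand check on the proportions: standard error = √(2 × 0.505 × 0.495 / 43) = 0.108; z = 0.19 / 0.108 = 1.76; power ≈ Φ(1.76 − 1.96) = 42%. A log-rank test restricted to responders has 6% power, so the loss comes from who is analysed.

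**(b) Proportional hazards.** The control weekly success probability is 1 − (1 − π)^(1/26), where π is the control response by week 26.

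| π | HR 2.0: t-test / log-rank | HR 1.6: t-test / log-rank |
|---|---|---|
| 44% | 9% / 66% | 7% / 35% |
| 60% | 17% / 78% | 9% / 44% |
| 80% | 42% / 85% | 18% / 52% |
| 95% | 76% / 88% | 40% / 57% |

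With weekly probability 0.15, control response is 1 − 0.85^26 = 98.5%. At HR 1.6 the powers are then 50% and 57%.

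**(c) Massage adds slow responders.** In both arms 41% respond at 0.35 per week, with mean 1/0.35 = 2.86 weeks. A further 19% respond only with massage, at 0.10 per week. By week 26, 0.19 × (1 − 0.9^26) = 17.8% of the massage arm have done so, with mean 10 − 26 × 0.0646 / 0.9354 = 8.20 weeks. The massage mean among successes is (0.41 × 2.86 + 0.178 × 8.20) / 0.588 = 4.47 weeks, which is 1.6 weeks longer than control although massage helps. The t-test is significantly against massage in 17% of trials. Under proportional hazards this happens in about 1% or less.

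**(d) No effect, selective removal.** Half of the massage-arm children still soiling after week 8 are removed. Expected removals are 43 × (1 − π)^(8/26) / 2.

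| π | Removed of 43 | Massage mean shorter by | t-test falsely favours massage | Log-rank on retained children falsely favours massage |
|---|---|---|---|---|
| 60% | 16 | 2.1 weeks | 15% | 16% |
| 80% | 13 | 2.0 weeks | 19% | 21% |
| 95% | 9 | 1.5 weeks | 20% | 22% |

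The nominal rate is 2.5%. A log-rank test on all randomised children, censored at removal, rejects in about 5% of trials (two-sided).

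**Second model.** A separate simulation (4,000 trials per scenario) used gamma-distributed times with mean 8 weeks.

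- At 60% versus 90% success with equal speed, the t-test favours massage in 2.5% of trials and log-rank in 87%.
- If massage converts a further 30% of children late (mean 16 weeks), the t-test is significantly against massage in 44%, while log-rank favours massage in 59%.
- With no effect, if 80% of massage-arm children slower than 10 weeks are dropped, the t-test favours massage in 40%.
- If every child succeeds, with means of 8 and 6 weeks, both tests have 75% power.

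**Counts.** 27 + 58 + 86 = 171, but Subjects and methods says 170 were evaluated, and the Abstract says the 86 were those assessed for eligibility.

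**The case against.** The strongest reply is that nothing in the documents shows any of the 86 lacked a time. Subjects and methods lists the 27 and the 58 before it mentions randomisation. Read in that order, the losses came first, all 86 may have succeeded, and there is no differential removal between arms. This cannot be ruled out. But unresponsiveness to the protocol and non-completion of treatment can be seen only once treatment has started, and no run-in is described. Even on the benign reading the plan lacks a rule for a foreseeable outcome, and the result would hold only for responders.

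A second point is that 41% versus 60% at 43 per arm puts about 43 failures (25 + 17) inside the 86, whereas the unresponsive children are described as outside it. That is fair. If the 85 excluded children (27 + 58) were randomised, about 85 per arm is the coherent size, and the powers are then 5% and 68%.

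Third, lost power may seem moot when a significant result is already reported. Scenario (d) is the one that bears on that result, and its removal rule is assumed because exclusions by arm are not given.

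Fourth, a t-test on all randomised children, with 26 weeks assigned to those still soiling, would recover most of the power: 40% versus 40% for log-rank in (a), and 61/72/82/88% versus 70/78/85/89% at HR 2.0 (1,500 trials each). This confirms that the analysis set and the missing rule are the main defects. Log-rank still gains up to about 10 points.

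Fifth, censoring a child removed as unresponsive is informative if removal depends on prognosis. True, but counting such children as still soiling rejects against massage in 13–18% of no-effect trials under the removal in (d). It therefore belongs in a sensitivity analysis.

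**Conclusion.** The concern holds. It is certain from the text that the planned comparison has no place for a child who does not stop soiling, and that no planned analysis shows how many in each arm did. The size and direction of any bias in this trial cannot be computed, because response rates and exclusions by arm are not given.

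Under the stated assumptions the loss of power ranges from small (50% versus 57% at 98.5% control response) to nearly total (5% versus 41% when only the success rate differs). A false finding for massage can rise from 2.5% to 15–20% under selective removal. A result against massage needs the special case of added late responders. If the 27 and 58 left before randomisation and all 86 stopped soiling, there is no bias within the 86, and the result is conditional on response. The sponsor should correct this before the time comparison is relied on.

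**What to change.** For this outcome only, replace the t-test with Kaplan-Meier curves and a log-rank test on every randomised child by assigned arm. Include any randomised child later removed for unresponsiveness, non-compliance or non-completion.

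- **Event:** the first visit with no soiling. Report later recurrence separately.
- **Censoring:** 6 months or the last visit, with a sensitivity analysis that counts children removed as unresponsive as still soiling at 6 months.
- **Also report by arm:** the soiling-free proportion at 6 months, and the difference in restricted mean time to 6 months with its 95% confidence interval.
- **Dose:** the t-tests can stay.
- **Participant flow:** state whether the 27 and the 58 were randomised, and to which arm, and reconcile 171, 170 and 86. Reconcile the arm labels too, since Group A is the massage arm in the Abstract and the senna-only arm in the methods.
- **Fallback:** if excluded randomised children cannot be recovered, describe the result as conditional on response.

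For the 86 the cost is SAP wording and standard procedures. The real cost is retrieving assigned arm and visit dates for any of the 27 and 58 who were randomised, and the documents do not show that these were kept.

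### Optional improvement, not an error: the two senna dose outcomes are compared unadjusted in children aged 4 to 14, although age and weight were collected; the gain from adjusting is unknown and may be nil

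*Combined protocol and SAP*

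**What the plan says.** The Statistical analysis section sets out the between-arm comparison as "Using independent t-test to compare between massage group and without massage group for demographic data (age, weight, height, and BMI), constipation starting dose"; the same list ends with "constipation end dose, and time till not soiling variables". Body size enters in two ways only. It is summarised ("Quantitative descriptive statistics included the mean and standard deviation for demographic data (age, weight, height, and BMI" and so on), and it is tested between arms by the same t-test. No regression, analysis of covariance or other adjusted model appears anywhere. The rural and urban comparisons are t-tests within strata, not adjustment.

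The section on Group A shows how the doses arise. "Single 10 mg dose senna was given with the start of impaction", and then "senna dose was increased if needed by 10 mg/clinic visit/week till achieving no soiling". The plan records the dose reached and the time taken ("Documentation of both initial effective starting dose and the time slipped till no soiling"), and at six months "the effective ending dose (maintenance dose) was documented". The doses are therefore apparently analysed in mg, and no scaling of senna by weight is stated. Subjects and methods gives the age range as 4 to 14 years and says that 86 children were randomised.

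**The concern.** Body size varies widely between ages 4 and 14. If the mg dose a child ends up on tracks body size, part of the spread in the dose outcomes is predictable from data already in hand. An unadjusted t-test leaves that spread in the error term, so its confidence interval is wider than the data allow.

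The trial is small and names no primary outcome. Starting dose, end dose and time to no soiling are the only outcomes compared between arms by t-test. A baseline table can show that the arms differ in weight, but not how much of a dose difference goes with that. An adjusted estimate would answer this.

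**Working it through.** The documents give no sample size calculation, outcome SD or outcome-weight correlation, so there is no figure of theirs to reproduce. The check is what one covariate would buy.

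**Inputs**
- Total N = 86 (Abstract; Subjects and methods).
- 43 per arm: assumed, since arm sizes are not stated. The ratios and the break-even below depend on total N, not on the split.
- r, the within-arm correlation of outcome with covariate: not in the documents; shown from 0 to 0.5.
- Two-sided 95% intervals: assumed. The level of 0.05 is stated, the sidedness is not.

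**Formulas** (outcome in SD units, covariate taken as normal)
- Unadjusted SE = √(1/43 + 1/43) = 0.2157, with 84 df. Half-width of the 95% interval = 1.9886 × 0.2157 = 0.429 SD.
- Adjusted SE = 0.2157 × √[(1 − r²) × (N − 3)/(N − 4)] = 0.2157 × √[(1 − r²) × 83/82], with 83 df (t = 1.9890).

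| r | Adjusted SE | Unadjusted SE / adjusted SE | Adjusted half-width (SD) |
|---|---|---|---|
| 0 | 0.2170 | 0.994 | 0.432 |
| 0.3 | 0.2070 | 1.042 | 0.412 |
| 0.5 | 0.1879 | 1.148 | 0.374 |

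**Break-even.** Setting (1 − r²)(N − 3)/(N − 4) = 1 gives r = √[1/(N − 3)]. At N = 86 this is √(1/83) = 0.110. If the 27 non-completers came out of the 86, then 86 − 27 = 59 were analysed and it is √(1/56) = 0.134. A simulation of 40,000 trials with 43 per arm agrees: the adjusted-to-unadjusted variance ratio was 1.012 at r = 0, 0.998 at r = 0.11, 0.921 at r = 0.3 and 0.759 at r = 0.5.

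**Why the titrated starting dose should not be the covariate.** It is itself compared between arms as an outcome. Suppose massage lowered both doses by 0.5 SD and their within-arm correlation were ρ. The difference in end dose adjusted for starting dose would be expected at 0.5 × (1 − ρ): 0.25 SD at ρ = 0.5 and 0.10 SD at ρ = 0.8, instead of 0.50 SD. These effects and correlations are illustrations, not document figures.

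**Time to no soiling.** The weekly 10 mg steps tie this time to dose. A simulation assumed a dose need with mean 35 mg and SD 15 mg, rounded up to 10 mg steps at one step a week, and correlations of 0.3 and 0.6 between need and weight. With the rule followed exactly, the SE ratios were about 1.04 and 1.23, as for dose. With random variation of SD 7 days added they were about 1.02 and 1.14; with 28 days, about 1.00 and 1.01. Every one of these inputs is assumed.

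**The case against.** The strongest reply is that this is a preference. Unadjusted comparison of randomised arms is a legitimate choice, no statement in the documents is contradicted, and the quantity that decides the matter, r, is absent. The flat 10 mg start with 10 mg steps gives no support for a strong link between dose and weight. The study is finished and its results are reported, so any adjusted result is post hoc. It also adds to an analysis that already compares three outcomes overall and by area. All of that stands, and it is why the point is only a suggestion.

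A reader might infer more, in four ways that the documents do not support:
- *That the t-test is biased or the reported P < 0.05 is undone.* Randomisation makes the t-test valid, and nothing here shows that the conclusion would change.
- *That chance weight imbalance is a second harm beside lost precision.* It is the same effect. The shift from a typical (1 SD) imbalance is r × 0.2157, and 0.2157² = 0.2157²(1 − r²) + (r × 0.2157)². The unadjusted interval already covers it.
- *That time to no soiling would gain as much as the doses.* That holds only if the titration rule is followed exactly; with assumed random variation of 28 days almost nothing is left.
- *That adjustment would deal with the exclusions.* Subjects and methods reports "Twenty-seven children did not complete the treatment course, fifty-eight child excluded due to unresponsiveness or non-compliance to our protocol". With the 86 randomised, these sum to 27 + 58 + 86 = 171 against 170 evaluated, and their timing relative to allocation is unclear. This is a separate question that a covariate does not repair.

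**Conclusion.** The point holds as an optional, low-cost improvement for starting dose and end dose. With 86 analysed, adjusting for one covariate costs about 0.6% in standard error if r = 0. Leaving it out means a standard error 4% larger than it need be at r = 0.3 and 15% larger at r = 0.5. Below r of about 0.11 (0.13 with 59 analysed) no gain in expected precision is to be had.

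These figures assume one covariate, measured before treatment and chosen without reference to the results, and an approximately linear relation with the outcome. The actual correlation is unknown, so the gain is unknown and may be nil. The validity of the t-test itself rests on the children being analysed as randomised, which the flow counts do not settle.

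**What to change.** For starting dose and end dose, add a linear model with group and one pre-treatment covariate: weight if it was measured at baseline, otherwise age. Fix that choice without looking at outcomes or baseline p-values. Report the adjusted difference with its 95% confidence interval beside the unadjusted difference and its interval. Name the direction as massage minus no massage, because the Abstract and the methods label the arms A and B in opposite order. Label the adjusted results post hoc and keep the t-test as the described analysis. Do not use the titrated starting dose as a covariate.

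The same model may be run for time to no soiling, with the note that the expected gain is smaller and may be negligible.

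The cost is two models on data already collected, one degree of freedom in each, and two further post hoc estimates, which should be read as sensitivity results and not as new tests.

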Official Title of Study: -

**MASSAGE WITH SENNA-BASED LAXATIVES VERSUS
SENNA-BASED LAXATIVES IN MANAGING OVERFLOW
RETENTIVE STOOL INCONTINENCE IN PEDIATRICS: A
Randomized Controlled Trial**

Document Date: - 02/12/2020.

**Human Subjects protection review board approval
date: - 03/31/2019**

MASSAGE WITH SENNA-BASED LAXATIVES VERSUS SENNA-BASED LAXATIVES IN MANAGING OVERFLOW RETENTIVE STOOL INCONTINENCE IN PEDIATRICS: A Randomized Controlled Trial

[name]

Assistant Lecturer of pediatric surgery, faculty of medicine, *South Valley University, Qena, Egypt*

[name].

Lecture of physical therapy. Department of Physical Therapy for Pediatrics, Faculty of Physical Therapy, South Valley University, Qena, Egypt

Abstract

Background: Overflow retentive stool incontinence is a common disorder affecting children that affect the quality of life in the form of shame, humiliation, depression, and decrease reduced self-esteem of children. **Aim:** To compare the effect of massage with senna-based laxatives versus senna-based laxatives in managing overflow retentive stool incontinence in pediatrics. **Methods:** Eighty-six children with overflow retentive stool incontinence enrolled in this study and were assessed for eligibility. Children's age ranged from four and fourteen. They were assigned randomly into two groups. Group (A) received abdominal massage with senna-based laxatives and group (B) received senna-based laxatives only. The application of massage was applied for 15 minutes, three times/day for six successive months. **Results:** Post-treatment there was a significant improvement in both groups in favor of massage group, $P < 0.05$. **Conclusion:** Abdominal massage with senna-based laxatives has a great effect on children with overflow retentive stool incontinence than senna-based laxatives only. **Keywords:** Overflow retentive stool incontinence, senna-based laxatives, and abdominal massage.

Introduction

Constipation is the most common colonic motility disorder in children affecting between 0.7% to 29.6 % of the pediatric population (**Rasquin 2006, Mugie 2011**) and is frequently associated with fecal incontinence secondary to overflow (**Voskuijl 2004**)

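### Massage is tested on three unranked outcomes, overall and within each area, all at P≤0.05 with no error control; the within-area tests also cannot show that its effect differs by area

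*Combined protocol and SAP*

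**What the plan says.** The Statistical analysis section sets out the comparison of the arms as follows: "Using independent t-test to compare between massage group and without massage group for demographic data (age, weight, height, and BMI), constipation starting dose", with end dose and time to no soiling completing the list. It then adds subgroup comparisons on the same three variables: "Also, to compare between two groups (massage group and without massage group) within the rural area and urban area". One significance rule covers everything: "All statistical analyses were significant at the level of probability" of P≤0.05. Nowhere do the documents name a primary outcome, order the outcomes, adjust for multiple testing or describe a group-by-area analysis.

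Starting dose is an outcome here, not a baseline value. The treatment text under the senna-only group says "senna dose was increased if needed by 10 mg/clinic visit/week till achieving no soiling", and then "Documentation of both initial effective starting dose and the time slipped till no soiling". Both variables therefore come out of the same titration, after treatment has begun.

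The Abstract reports "Post-treatment there was a significant improvement in both groups in favor of massage group" at P<0.05 and concludes: "Abdominal massage with senna-based laxatives has a great effect on children with overflow retentive stool incontinence than senna-based laxatives only". Neither sentence says which outcome is meant, and neither mentions area.

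**The concern.** There are two separate points.

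1. **Error rate.** If superiority can be claimed from any one of several tests, each at 5%, the chance of a false claim exceeds 5%. Because the Abstract names no outcome, any one of the three overall tests could carry its claim under the stated rule, and a reader cannot tell which did.

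2. **Area.** Testing massage separately in rural and in urban children asks, in each area, whether the effect is distinguishable from zero. It does not ask whether the two effects differ. A significant result in one area beside a non-significant one in the other is easily read as an area difference, although it is common when the true effect is the same in both. This point is about interpretation and adds nothing to the error rate in point 1.

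**Working it through.** The plan gives no power, effect size, SD or family-wise error rate, so there is no figure of its own to reproduce.

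**Inputs from the documents.** There are three outcomes, two areas, P≤0.05 per test and 86 children randomised.

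**Assumptions.** I took 43 children per arm (86/2), two-sided pooled t-tests, 25 and 18 children per arm in the two areas, and equal correlation between outcomes from 0 to 0.99.

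**Count.** There are 3 overall tests plus 2 areas × 3 outcomes = 6, giving 9 tests of massage. The rural-versus-urban comparisons within each arm are left out because they do not test massage.

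**Point 1: independence bound.** For k independent tests the chance of at least one false positive is 1 − 0.95^k.
- k = 3: 1 − 0.95³ = 14.3%.
- k = 9: 1 − 0.95⁹ = 37.0%. This overstates the risk, because the overall tests reuse the children in the area tests, so the nine-test case was simulated.

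**Point 1: simulation with no true effect** (40,000 trials per cell):

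| Outcome correlation | 0 | 0.5 | 0.8 | 0.95 | 0.99 |
|---|---|---|---|---|---|
| Any false positive, 3 tests | 14% | 13% | 10% | 7% | 6% |
| Any false positive, 9 tests | 30% | 27% | 22% | 17% | 14% |
| False result favouring massage, 3 tests | 7% | 6% | 5% | 4% | 3% |
| False result favouring massage, 9 tests | 16% | 14% | 11% | 9% | 7% |

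The nominal values are 5% for the first two rows and 2.5% for the last two. A repeat run gave 31% for nine tests at zero correlation. Area splits of 22/21 and 30/13 move the figures by at most about 1 point.

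**Point 1: allowing for the shared titration.** Starting dose and time to no soiling may be almost one variable. With those two correlated 0.9999, and end dose correlated 0.5, 0.8 or 0.95 with both:
- Any false positive: 9, 8 and 6% (3 tests); 20, 18 and 15% (9 tests).
- False result favouring massage: 5, 4 and 3% (3 tests); 10, 9 and 7% (9 tests).

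**Point 2: same true effect in both areas.** With power p₁ and p₂ in the two areas, the chance that exactly one is significant is p₁(1 − p₂) + p₂(1 − p₁). At 0.61 SD, the effect for which 43 per arm gives 80% power overall, p₁ = 56% and p₂ = 43%. Then 0.56 × 0.57 + 0.43 × 0.44 = 0.319 + 0.189 = 0.51.

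| Common effect (SD, assumed) | 0.2 | 0.4 | 0.61 | 0.8 | 1.2 |
|---|---|---|---|---|---|
| Exactly one area significant | 18% | 38% | 51% | 42% | 7% |

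Over splits from 22/21 to 30/13 the five values are 18%, 37–39%, 50–55%, 40–50% and 6–17%.

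**The case against.** The strongest counter-arguments, and what stands of each:

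- **No area claim is made.** The aim, result and conclusion do not mention area, and the purpose of the within-area tests is not stated. This stands. Point 2 is a risk of misreading and not a demonstrated error, and its percentages mostly reflect low power within an area.
- **The nine-test figures do not bear on the Abstract's claim, which is for massage overall.** This stands. They show only what the stated rule permits; the three-test figures are the relevant ones.
- **The outcomes are correlated, so the excess is small.** This largely stands. Zero correlation is implausible for starting dose and time, and 3–5% against 2.5% is a modest excess. It is still an excess, and the outcome behind the claim remains unnamed at any correlation.
- **All three outcomes may have been significant.** The document has no results table, so this cannot be excluded. Had the claim required all three, there would be no inflation. Nothing in the plan sets that requirement.
- **Holm is only one option, is applied late, and is conservative for correlated outcomes; naming the outcomes and giving confidence intervals would cost no power.** Naming and intervals remove the ambiguity, but they do not control the error of a claim that rests on significance. A single primary outcome would hold the error at 5%, but choosing it now could not be shown to be independent of the results. Holm treats the three outcomes alike and avoids that choice.

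**Conclusion.** Both points hold. Nine tests of massage are judged at P≤0.05 with no ranking or adjustment, and superiority is claimed without an outcome. For the three overall tests the chance of any false positive is about 6–14% against 5%. False superiority of massage is about 3–7% against 2.5%, or 3–5% if starting dose and time are near-duplicates. Over all nine tests the rule permits 14–31% and 7–16% respectively.

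The within-area tests cannot show whether the massage effect differs by area. With a common effect of 0.2 to 0.8 SD, exactly one area is significant in about 18–51% of trials.

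The counts and the missing adjustment are plain from the text. The sizes rest on assumed arm sizes, area split, correlations and effects, and should be read as ranges. The matter should be corrected, but the excess error behind the Abstract's claim is modest.

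**What to change.** **Overall claim.** Base superiority on the three overall comparisons with Holm: smallest P against 0.05/3 = 0.0167, next against 0.05/2 = 0.025, last against 0.05. Name the outcome or outcomes that pass. In the same simulations this brings any false claim to 2–5% and false superiority to 1.0–2.5%. Two statements must accompany it:
- Holm was applied after results were known, so it is not prospective control.
- It assumes that the analysed groups are the groups as randomised. The Subjects and methods section reports 27 non-completers and "fifty-eight child excluded due to unresponsiveness or non-compliance to our protocol", without making clear whether they were removed before or after randomisation. That is a separate question, and Holm does not answer it.

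**Area.** Replace the within-area significance tests with one group × area linear model per outcome. Report the interaction estimate and the area-specific massage differences, each with a 95% CI. Label them exploratory and make no significance claims: three interaction tests at 0.05 each would themselves give at least one false interaction in 6–14% of trials. State that an interaction interval containing zero does not prove equal effects.

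**Cost.** This needs revised wording and re-analysis of existing data; no new data are required.
- If massage affects one outcome only, by 0.61 SD (assumed), power at the first Holm step falls from about 80% to 65%.
- If it affects all three by 0.61 SD, the chance of at least one claim falls from 95% to 87% at correlation 0.5, from 90% to 79% at 0.8, and from 85% to 72% at 0.95.
- Area estimates will be imprecise. With the 25/18 split, the 95% CI half-widths are about 0.57 and 0.68 SD within areas and 0.87 SD for the interaction, against 0.43 SD overall.
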